## 6.5 Description and justification of route of administration and dosage

Dose-adjusted acenocoumarol once daily, titrated to the pre-specified INR target range, with oral tablets of either 0.5 milligrams of acenocoumarol (intervention group), or the regular 1.0 milligram tablets (control group).

## 6.6 Dosages, dosage modifications and method of administration

As mentioned before, the sensitivity for VKA can differ between patients and also over time within patients. Frequent INR-measurements are required to achieve an anticoagulant effect within the target range. The frequency of monitoring depends on the stability of INRs, but can also be intensified due to changes in health status such as the need for invasive procedures or changes in co-medication. In case of under- and over-anticoagulation the dosage can be adjusted; for extreme over-anticoagulation vitamin K supplementation can be used. The procedures for this are laid down in protocols by the Thrombosis Services, and will not differ from regular care.

## 6.7 Preparation and labelling of Investigational Medicinal Product

Participants in the control group will get their regular 1 mg tablets with regular labelling from their usual out-patient pharmacy.

Details on preparation and labelling for participants in the intervention group, i.e. about tablets with 0.5mg of acenocoumarol, will be attached.

## 6.8 Drug accountability

The University Medical Center Groningen pharmacy will manufacture and label tablets of acenocoumarol in 0.5 milligrams in accordance with the guidelines of ICH-GCP[17] and ICH-GMP[7]. The drug will be picked up at the pharmacy by study personnel, who will then distribute it to subjects. Unused drugs will be returned to the pharmacy.

We will not perform any drug accountability for subjects in the control group. The Thrombosis Service routinely collects patient-reported data on acenocoumarol compliance.

# 7. Non-investigational product

---

No non-investigational products will be used in this study.

## 8. Methods

---

### 8.1 Study parameters/endpoints

#### 8.1.1 Main study parameter/endpoint

The main study endpoint is **quality of anticoagulation**, assessed using the following parameters:

- Individual time in therapeutic range (iTTR) Calculated using the Rosendaal method[18]
- INR variability Calculated using the Variance Growth Rate[19] and the SDTinr[20]

#### 8.1.2 Secondary study parameters/endpoints (if applicable)

The secondary study parameters are **treatment satisfaction, medication errors and number of INR measurements**.

Treatment satisfaction will be assessed using the PACT-Q2 questionnaire[6].

Medication errors are routinely collected by the Thrombosis Service. These will be analysed on number and category of error.

All dates of INR measurements are routinely collected by the Thrombosis Service, so we can easily calculate the number of INR measurements.

### 8.2 Randomisation, blinding and treatment allocation

The study personnel will perform randomisation on-the-spot. To avoid technical difficulties, we will perform randomisation using ordered envelopes. We will stratify by INR target range (2.0-3.0 versus 2.5-3.5) within pre-specified blocks. The University Medical Center Groningen Pharmacy will provide randomisation lists.

Patients and professionals at the thrombosis service will know to which treatment group the patient has been randomised.

## 8.3 Study procedures

Visit	Regular visit	Study visit	[...] †	6 months
Age and VKA dose	X			
Information letter	X			
Informed consent		X		
Check of participation criteria		X		
Randomisation		X		
PACT-Q2		X		X
Start allocated treatment		X		
Follow-up data * §			X	X
INR measurement *	X	X	X	X
Possible dose adjustment *	X	X	X	X

\* All items marked are (also) performed for usual care. † Every regular INR measurement, based on the previous INR values and change in co-medication etc., based on the regular algorithm of the Thrombosis Service. § Follow-up data is the information that is routinely collected by the thrombosis service, e.g. change in co-medication, planned surgical procedures, bleeding complications and errors in medication intake.

## 8.4 Withdrawal of individual subjects

Subjects can leave the study at any time for any reason if they wish to do so without any consequences. The investigator can decide to withdraw a subject from the study for urgent medical reasons.

## 8.5 Replacement of individual subjects after withdrawal

We will not replace individual subjects.

## 8.6 Follow-up of subjects withdrawn from treatment

Patients who want to withdraw consent will be asked to attend an end-of-study visit. If they refuse, the study time of that specific patient will end retrospectively at the last attended study-visit.

Another situation that can lead to implicit withdrawal is loss to follow-up. In case of loss to follow-up, the general practitioner and/or referring physician will be contacted to find out whether the patient died, has moved or any other explanation. If the contact can be fully restored all study time is taken into account, otherwise the study time of that specific patient will end retrospectively at the last attended study-visit.

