## Nature and extent of the burden and risks associated with participation, benefit and group relatedness

Patients already use dose-adjusted acenocoumarol, so we do not expect an added risk caused by the drug. All patients will be visited and administered a short questionnaire twice for the study. The intervention group will on average have to take twice as many tablets of acenocoumarol as before. This research will yield data relevant for the participating patients and other, similar patients.

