## 11.4 Benefits and risks assessment, group relatedness

For **usual care**, all participants are exposed to the benefits and risks of anticoagulation, because their treating physician considered the benefit (protection against thrombosis) to outweigh the risk (bleeding). The pharmacological compounds used in this study are registered for this indication. All participants need to have regular blood collections for regular care.

For **this study**, all patients will have two (extra) visits by research personnel where they will fill in a questionnaire. Patients in the *intervention group* have the disadvantage that they have to take more tablets, possibly at the advantage of a more stable dosing rhythm.

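### Section 8.6 gives zero study time to leavers who refuse the end visit or stay lost to follow-up, although their INRs are recorded in routine care

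*Protocol*

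**What the plan says.** Protocol section 8.6 deals with two kinds of early leaver.

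- **Consent withdrawn.** "Patients who want to withdraw consent will be asked to attend an end-of-study visit". For those who decline, "If they refuse, the study time of that specific patient will end retrospectively at the last attended study-visit".
- **Loss to follow-up.** The general practitioner or referring physician is asked what happened; death is one of the explanations named. Patients with whom contact is re-established in full keep all of their time. For the rest, the section reads: "otherwise the study time of that specific patient will end retrospectively at the last attended study-visit".

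On the number of study visits, the Summary states: "All patients will be visited and administered a short questionnaire twice for the study". Section 11.4 agrees: "all patients will have two (extra) visits by research personnel where they will fill in a questionnaire". The schedule in section 8.3 puts consent, randomisation and start of treatment in a column labelled *Study visit*. The next study contact is at 6 months, and the column between them is for regular INR measurements.

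On the data, section 8.1.2 states: "All dates of INR measurements are routinely collected by the Thrombosis Service". It says that medication errors are also collected routinely. Section 8.5 adds: "We will not replace individual subjects".

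**The concern.** A cut-off at the last attended study visit is reasonable when outcomes are measured at study visits. Here they are not. INRs come from usual care between two widely spaced study visits, so the rule ties the end of observation to a schedule unrelated to the outcome data. For the patients it reaches, everything recorded between randomisation and leaving is set aside.

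Two things are at stake. First, the comparison moves towards completers only. The trial is open-label, the intervention group takes on average twice as many tablets (Summary), and the patients are 80 or older, so leaving could depend on both the arm and the quality of anticoagulation. Second, the main objective is to collect data on effect size, and section 10 sizes the full trial on the effect found here. A distortion in the pilot estimate would carry forward even though the pilot does no formal testing.

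**Working it through.** **Step 1: what the rule does.** Treatment starts on the day of randomisation and runs to the 6-month visit (section 3). The study visits are randomisation and month 6 (Summary, sections 8.3 and 11.4). A patient who leaves in between, without an end visit and without restored contact, last attended a study visit at randomisation. Study time = randomisation date − randomisation date = 0. The main endpoint parameters in section 8.1.1 (iTTR by the Rosendaal method, Variance Growth Rate, SDTinr) need INRs over time after randomisation, so none can be computed. INR counts and medication errors are lost too.

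**Step 2: who is reached.**

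| Route out | Cut-off in section 8.6 | Study time |
|---|---|---|
| Withdraws consent, attends end visit | Not triggered | Kept |
| Withdraws consent, refuses end visit | Last attended study visit | Zero |
| Lost, contact fully restored | None | All kept |
| Lost, contact not restored (on the plain reading, also those found on tracing to have died) | Last attended study visit | Zero |
| Death known directly; withdrawal by the investigator (section 8.4) | None stated | Open |

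**Step 3: the plan's own figure, as a check on the inputs.** Section 4.4 gives TTR 69% (SD 19) and 72.5% (SD 17), alpha 5% (two-sided assumed), power 80% and failure rate 10%. Common SD = √((19² + 17²)/2) = 18.03. Per arm: 2 × (18.03 × (1.960 + 0.842)/3.5)² = 416.5; total 832.9; × 1.10 = 916.2, rounded up to 917. This matches the stated 917. The present point does not change that figure.

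**Step 4: how much is lost.** No dropout rate is stated for the pilot. Assume that every leaver falls under the rule, that leaving is uniform over 6 months (mean 3 months each), and that leavers are split equally between arms. With N = 80 and dropout d, patients lost = 80d, patient-months lost = 80d × 3, and accrued = 80(1 − d) × 6 + 80d × 3. Half-width of the 95% interval for the iTTR difference = 1.96 × 18.03 × √(2/m), with m patients per arm.

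| d | Patients lost | Patient-months lost | m | Half-width |
|---|---|---|---|---|
| 0% | 0 | 0 | 40 | 7.9 |
| 5% | 4 | 12 of 468 (2.6%) | 38 | 8.1 |
| 10% | 8 | 24 of 456 (5.3%) | 36 | 8.3 |
| 20% | 16 | 48 of 432 (11.1%) | 32 | 8.8 |

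The 10% row uses the failure rate that section 4.4 gives for the follow-up study.

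**Step 5: possible bias.** In one arm, completers' mean − mean of all randomised = p × g, where p is the proportion leaving and g is completers' iTTR minus leavers' iTTR. Bias in the difference between arms = p₁g₁ − p₀g₀. No value of p or g is in the protocol, so these are assumptions:

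- equal leaving and equal gap: 0;
- 15% versus 5%, gap 10: 0.15 × 10 − 0.05 × 10 = 1.0 point;
- 15% versus 5%, gap 15: 2.25 − 0.75 = 1.5 points;
- 15% versus 5%, gap 20: 3.0 − 1.0 = 2.0 points.

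The sign reverses if controls leave more often. The assumed difference in section 4.4 is 72.5 − 69 = 3.5 points.

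**The case against.** **Is a regular INR contact a study visit?** The term is not formally defined, and the column of regular INR measurements sits in the visit row of the section 8.3 schedule. If those contacts count, the rule already ends study time close to the last INR and little is lost. Ending study time retrospectively also sounds more natural with several visits than with one. But section 8.3 labels its columns *Regular visit* and *Study visit* separately, and the Summary and section 11.4 both count two visits. The strict reading is the plain one. If the lenient reading was meant, the text still has to say so.

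**Does every early leaver lose all data?** A reader might infer this. Section 8.6 does not support it: an attended end visit or fully restored contact takes the patient out of the rule. Nor does the text set study time to zero for all deaths or for withdrawals by the investigator. For deaths known directly and for investigator withdrawals it is silent.

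**Is 10% the pilot's dropout rate?** Section 4.4 gives it for the larger follow-up study and does not define failure as dropout. Eight of 80 is therefore an illustration, and it also assumes that no leaver attends the end visit or is traced.

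**Is a material bias shown?** No. The leaving rates and the gap are assumed, and zero is within the range. Even 2 points is well below a half-width of about 8. This objection stands and limits the severity. It does not justify the rule, because the loss is avoidable and the point estimate is what section 10 carries forward.

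**Is this a matter for the statistical analysis plan?** The protocol does not leave the cut-off open; it fixes it. A plan that follows the protocol inherits it.

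**Conclusion.** The concern holds for a defined group: patients who withdraw consent and refuse the end visit, and patients who stay lost to follow-up, including on the plain reading those found on tracing to have died. For them the rule in section 8.6 discards recorded on-treatment outcome data for no analytic gain.

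The number affected is unknown. It would be 4 to 16 of 80 at an assumed dropout of 5 to 20% if all leavers fell under the rule, and fewer if some attend the end visit or are traced. Bias in the iTTR difference ranges from zero to about 1 to 2 points under the assumptions shown, and the loss of precision is modest. In a pilot without formal testing this should be fixed, but it does not undermine the trial. The case for acting is that the rule is wrong as written, the data already exist, and the estimate will be used to size the full trial.

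**What to change.** Reword section 8.6 so that study time ends at the last INR recorded by the Thrombosis Service on or before withdrawal of consent, death or loss of contact, and so that all data to that date are analysed in the randomised group. State the cut-off also for deaths known directly and for withdrawals by the investigator, where the section is now silent.

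Optionally, where consent allows, ask patients who decline the end visit whether their routine INR data may be used to month 6.

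Two limits should be accepted. Very early leavers may have too few INRs for iTTR or the variability measures. The change in treatment satisfaction still needs the end-visit questionnaire, so this rewording does not recover it.

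The cost is protocol wording, matching wording in the analysis plan, and possibly a line in the consent form, which is not among the pages at hand. No new data collection is needed. The change should be made before database lock.

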## 8.7 Premature termination of the study

There are no pre-specified criteria for premature termination of the study.

## 9. Safety reporting

---

### 9.1 Temporary halt for reasons of subject safety

In accordance to section 10, subsection 4, of the WMO, the sponsor will suspend the study if there is sufficient ground that continuation of the study will jeopardise subject health or safety. The sponsor will notify the accredited METC without undue delay of a temporary halt including the reason for such an action. The study will be suspended pending a further positive decision by the accredited METC. The investigator will take care that all subjects are kept informed.

### 9.2 AEs, SAEs and SUSARs

#### 9.2.1 Adverse events (AEs)

Because acenocoumarol is a registered medicine with which there is ample experience, we will not collect any non-serious adverse events.

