# 1. Introduction and rationale

---

40% of patients using anticoagulation (VKA) is eighty years or older. Their share will further increase because the population ages, and indications for anticoagulation are more often acknowledged. However, the elderly are a vulnerable group. The risks of both haemorrhages and thrombosis increase with age (70% increase of those aged 75 and older, compared with those under 75 [1]). The HARM investigation[2] showed VKA are one of the most dangerous medication groups for medication-related hospitalisation.

Good anticoagulation control optimises the benefits and minimises the risks. Parameters such as time spend in therapeutic range (iTTR) and variability are a strong intermediary for clinical outcomes [3,4]. Good quality of anticoagulation is therefore of paramount importance.

Unfortunately, our own research shows that quality of anticoagulation decreases with age[5]. This is also true amongst the elderly: patients aged 80 and above are worse controlled than those aged 70-79. A possible cause is the diminishing acenocoumarol dose required with higher age. In our study it declined from on average 2.3mg in patients aged 70-79, to 1.9mg for those aged 80-89, to 1.6mg for those aged 90 or older[5]. This has to do with nutritional state, body composition and comorbidity. Because acenocoumarol is only available in tablets of 1 milligram, it is harder to spread out low doses over the week evenly. The scheme 1-2-1-2 causes larger relative differences than 2-3-2-3. Indeed, in our data we saw a lower iTTR but above all a higher variability in patients using less than 2 milligrams of acenocoumarol per day, versus those with a higher dosage.

In other words, usual care for elderly does not achieve the same quality as for younger patients, despite higher commitment of the thrombosis service, more frequent INR controls and more home visits. These interventions cost money, and -more importantly- lower quality of anticoagulation causes more thrombotic complications and haemorrhages[3,4]. Patients in the lower quarter of anticoagulation control are three times as prone to thrombotic complications or haemorrhages as the other 75%[3].

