## 3. Study design

---

We propose an open-label, prospective, randomised controlled trial.

Many patients visit, or are visited by, the Thrombosis Service regularly for INR measurements. A day later they will receive a new dosing calendar via regular mail, with an overview of the daily dosages in the period until the next INR measurement. Potentially eligible patients selected by the Thrombosis Service (based on age and acenocoumarol dose) will be handed out an information letter about our study and a response card during one of these regular visits. Patients who express their interest in participating in the study will be visited by research personnel to inform them about the study, answer all questions, and collect informed consent. After consent, the subject will be randomised into one of two groups:

- **Intervention group:** dosing using tablets of 0.5 mg acenocoumarol
- **Control group:** dosing using the regular tablets of 1.0 mg acenocoumarol

Allocated treatment will begin the same day, and will last until the end of study visit six months later. The system of “therapy control” with INR-based dosage adjustments will not differ from everyday care in both treatment groups, only the dosing steps might differ. Directly following randomisation, and during the end-of-study-visit, subjects will fill in the PACT-Q2 questionnaire[6], a questionnaire developed specifically to assess patients’ perception of anticoagulation treatment.

We opt for a RCT (instead of for instance a before and after comparison) to avoid the “Hawthorne effect” (the phenomenon that quality would improve simply because one participates in a study). Due to the nature of the medication and its monitoring, it would be very difficult to do this in a blinded fashion. Because we use an objective endpoint, we do not foresee bias there. For the subjective measurements of patient satisfaction, unblinded assessment is crucial as the larger number of tablets is inherent to the intervention.

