## 4.4 Sample size calculation

We performed a power analysis for a larger follow-up study, based on the following parameters:

Parameter	Value	Standard deviation
TTR control group	69 %	19
TTR intervention group	72.5%	17
Alpha (type I error rate)	5 %	
Failure rate	10 %	
Power (1 - type II error rate)	80 %	

The TTR values above are based on observational findings in our clinical practice. It should however be noted that the INR target ranges have been modified (c.q. narrowed) as per January 1st, 2016, and that we expect this will affect the TTR in both groups. This underlines the necessity of a pilot study.

This resulted in a needed sample size of 917 patients, which is much less than the 140 000 patients aged 80 and above managed by the Dutch Thrombosis Services.

For this pilot study we want to randomise 2 x 40 patients. This should give us an overview of the point estimates in the power analysis (which are currently based on observational data), and -more importantly- about the time investment needed to conduct a larger-scale study. Due to the inter-individual variation in response to VKA, we think a smaller sample could distort the view.

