### 5.1 Investigational product/treatment

Both treatment groups will be treated with acenocoumarol:

- the control group will be treated with regular, registered 1 mg tablets ([Summary of the Product Characteristics](#)).
- for the intervention group, tablets of 0.5 milligrams will be manufactured by the UMCG Pharmacy in accordance with ICH-GMP[7] and the regulations imposed by the WMO and the *Geneesmiddelenwet*.

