### 9.4 Follow-up of adverse events

All AEs will be followed until they have abated, or until a stable situation has been reached. Depending on the event, follow up may require additional tests or medical procedures as indicated, and/or referral to the general physician or a medical specialist. SAEs need to be reported until end of study within the Netherlands, as defined in the protocol.

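### Section 9.2.1 excludes non-serious adverse events for a reason that does not cover the pharmacy-made 0.5 mg tablet, contradicts 9.4 and 8.3, and leaves routinely recorded bleeds without a stated use

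*Protocol*

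**What the plan says.** Section 9.2.1 gives both the rule and its reason: "Because acenocoumarol is a registered medicine with which there is ample experience, we will not collect any non-serious adverse events". Section 9.2.2 keeps every serious adverse event, including deaths, life-threatening events and non-elective hospital admissions.

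Four other places bear on that rule.

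- **Status of the tablets.** Section 1 builds the rationale on the statement "Because acenocoumarol is only available in tablets of 1 milligram". Section 5.1 says "the control group will be treated with regular, registered 1 mg tablets", whereas for the intervention group "tablets of 0.5 milligrams will be manufactured by the UMCG Pharmacy". Section 6.8 confirms the local manufacture.
- **Follow-up of events.** Section 9.4 says "All AEs will be followed until they have abated, or until a stable situation has been reached", with no restriction to serious events.
- **Routine data.** The note to the schedule in 8.3 names, among the information the Thrombosis Service records as usual care, "planned surgical procedures, bleeding complications and errors in medication intake". The schedule marks this follow-up for the regular INR contacts and the six-month visit.
- **Use of the data.** Section 8.1 lists iTTR, INR variability, treatment satisfaction, medication errors and number of INR measurements. Section 10 describes the anticoagulation parameters, satisfaction and medication errors, and then sizes the full trial. Bleeding is in neither list.

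**The concern.** The reason in 9.2.1 concerns the compound, while the trial tests a product. What is new is a tablet strength made for the study and a regimen in which, according to the Summary, patients take on average twice as many tablets. The third aim in Section 2 is open to the possibility that smaller units cause intake errors. With a vitamin K antagonist, such an error may show itself as a bleed or a thrombosis. Long experience with 1 mg tablets does not settle that question.

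The rule is also hard to apply beside its neighbours. Under 8.3 a non-serious bleed is follow-up data. Under 9.2.1 it is an adverse event that the study does not collect. Under 9.4 it is an event to be followed until it resolves or stabilises. Staff and analysts cannot tell from the protocol which instruction governs.

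At stake is a simple description of bleeding by arm, from records that already exist, in patients aged 80 and above. Medication errors come from the same routine source and were made a secondary endpoint. Bleeding was not.

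**Working it through.** **Step 1: does the stated reason reach the test product?**

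| Feature | Control arm | Intervention arm |
|---|---|---|
| Active substance (6.4) | acenocoumarol | acenocoumarol |
| Tablet (5.1) | 1 mg, registered | 0.5 mg, made by the hospital pharmacy |
| Supply (6.7, 6.8) | usual out-patient pharmacy | hospital pharmacy, through study personnel |

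The reason holds for the substance and for the control product. It does not hold for the 0.5 mg tablet. Section 9.2.3 itself separates authorised from unauthorised products when it names the reference safety document. Section 13.2 repeats the reasoning of 9.2.1 by relying on registered compounds.

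**Step 2: do 9.2.1, 9.4 and 8.3 agree?** An event that is not collected cannot be followed to resolution, so 9.2.1 and 9.4 conflict as worded. They agree only if 9.4 means all recorded adverse events, which it does not say. Sections 9.2.1 and 8.3 agree only if a bleed in the Thrombosis Service's file is not treated as a study adverse event, which is not said either.

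**Step 3: how much can major bleeds alone show?** The protocol states no expected number of bleeds, so there is no figure to reproduce. Its inputs are:

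- size, from 4.4: "For this pilot study we want to randomise 2 x 40 patients", so 80 patients;
- duration, from Section 3: treatment "will last until the end of study visit six months later", so 0.5 year;
- major bleeding rate, from 6.4: 1.40 to 3.40% per year.

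Patient-years = 80 × 0.5 = 40, or 20 per arm. Expected events = patient-years × rate, and the Poisson probability of none is exp(−expected).

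| Rate per year | Expected, both arms | P(none in trial) | Expected per arm | P(none in a given arm) |
|---|---|---|---|---|
| 1.40% | 40 × 0.014 = 0.56 | 0.57 | 0.28 | 0.76 |
| 3.40% | 40 × 0.034 = 1.36 | 0.26 | 0.68 | 0.51 |

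Two sensitivity checks, both resting on assumptions:

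- Suppose the 10% failure rate listed in 4.4 for the larger study means that 8 of the 80 patients leave halfway. Follow-up is then 72 × 0.5 + 8 × 0.25 = 38 patient-years, giving 0.53 to 1.29 events.
- Section 6.4 says the risk rises with age. If the upper rate is raised by the 70% age difference quoted in Section 1, it becomes 3.40% × 1.7 = 5.78%, and 40 × 0.0578 = 2.3 events, with P(none) = 0.10.

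Precision is poor throughout. No events in one arm gives a one-sided 95% upper limit of about 3.0/20 = 15 per 100 patient-years. One event in the whole trial gives an exact 95% interval of about 0.06% to 14% per year.

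**Step 4: what does 9.2.1 itself leave out?** This cannot be calculated, because the protocol gives no rate for non-serious bleeds or other non-serious events. The counts in step 3 show how little serious bleeding can tell. They do not measure the loss caused by 9.2.1.

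**The case against.** The strongest reply is that limiting collection to serious events is a defensible choice in a small pilot of a long-used compound. The substance is the same in both arms (6.4), every patient has used it for at least nine months (4.3), the tablets are made to GMP (5.1, 6.8), and INR-guided dosing would be expected to expose a potency problem. Serious unexpected reactions remain reportable. This stands as a defence of not running full adverse event collection. It does not make the registration argument true of the 0.5 mg tablet.

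Second, major bleeds would ordinarily qualify as serious under 9.2.2, so collecting non-serious events would leave their expected number essentially unchanged. That is correct. The scarcity comes from the size and length of the pilot.

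Third, a descriptive safety table can be left to the statistical analysis plan, which Section 10 announces and which is not at hand, and 9.3 promises the ethics committee a complete safety analysis. This stands in part. However, the collection rule and the endpoint list belong to the protocol, 9.2.1 is an explicit exclusion rather than a silence, and 9.3 promises no comparison by arm.

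A reader might infer that the pilot's whole safety evidence rests on about one event. The documents do not support that. The count covers major bleeds only, and all serious events are collected. The protocol gives no rate for these. At assumed rates of 10 to 50% per year, 40 patient-years would give 4 to 20. Nor does it follow that non-serious bleeds are lost, since 8.3 has them recorded.

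**Conclusion.** The point holds as a matter of rationale, consistency and unused data. The reason in 9.2.1 does not cover the product under test. The rule contradicts 9.4 and 8.3 as they are written. Bleeds already recorded in both arms have no assigned use in the protocol. With 0.56 to 1.36 major bleeds expected in total, and a 26 to 57% chance of none, serious bleeding alone cannot say much by arm. These figures assume full follow-up and the rates in 6.4. The age adjustment tried above raises the upper count to about 2.3 and does not alter the conclusion.

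A reader might also infer that the pilot must supply a bleeding rate so that the full trial can be planned. It need not: the calculation in 4.4 rests on TTR, and the aims in Section 2 are anticoagulation quality, satisfaction and intake errors. The case for describing bleeds is that the data exist and bear directly on the safety of the new tablet. The change is worth making, but the gap does not threaten the pilot's main objective.

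**What to change.** 1. Reconcile 9.2.1 with 9.4 and 8.3: state which adverse events the study records, which of those are followed up, and how bleeds in the Thrombosis Service's file are classed.
2. Correct the rationale in 9.2.1, and the matching statement in 13.2, so that it acknowledges that the 0.5 mg tablet is pharmacy-made. Any decision to restrict collection should rest on grounds that apply to that product.
3. In 8.1.2, add bleeding complications recorded by the Thrombosis Service, serious or not, as a descriptive outcome in both arms. Add thromboembolic complications where the service records them; 8.3 does not name these, so availability should be checked first.
4. In Section 10, state that these are described by arm as the number of patients with an event and the rate per patient-year with a 95% confidence interval, without testing.

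The cost is protocol wording, extraction of fields already recorded, and one descriptive table. No visits or measurements are added. The intervals will be wide and should be presented as such.
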